4.1 Overview

This is a single-center, open-label, one-arm observational clinical study. Up to 120 subjects will be enrolled in the study. Each subject will participate in one session for a maximum of 3 hours, but typically

lasting an hour, including the preparation and consent process. Subjects will be monitored for AEs during and immediately following the procedure. Subjects will be requested to self-report any AEs for up to seven days following the procedure. The overall study duration is expected to be approximately 5 years

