15 REFERENCES

30

Revision History

Version Number	Description of Change	Effective Date
Version 1	Initial release	20 Mar 2017
Version 2		13 Feb 2018
Version 3		13 Aug 2019
Version 4		07 Oct 2021
Version 5-R		02-Mar 2022
Version 6-R		02-May-2022
Version A		01-Jun-2022

List of abbreviations

Abbreviation	Definition
ADE	Adverse device event
AE	Adverse event
CIR	Company-in-residence [REDACTED]
CRF	Case report form
FDA	Food and Drug Administration (United States)
[REDACTED]	[REDACTED]
GCP	Good clinical practices
ICF	Informed consent form
IFU	Instructions for use (User manual)
IRB	Institutional review board
NADPH	Reduced nicotinamide adenine dinucleotide phosphate
PHI	Protected Health Information
SADE	Serious adverse device event
SAE	Serious adverse event
UADE	Unanticipated adverse device effect
US	United States

Study summary

Title	Nonlinear imaging of skin in vivo
Protocol number	[REDACTED]
Phase	Feasibility
Methodology	Single center, open label, one-arm observational study
Study duration	Up to 5 years
Study center(s)	Single-Center, [REDACTED]
Objectives	
The overall objective of this study is to investigate the potential for the Vio™ to display microscopic skin structure in people of different age, sex, race, and skin health.

Aims	
Aim 1: Quantify imaging performance in various types of skin, which may include estimated in vivo resolution and imaging depth. Various types of skin includes skin of different people as well as skin in different locations on the body, and skin with skin disease, including basal cell carcinoma
 
Aim 2: Qualitatively evaluate image quality and interpretability by physicians trained in dermatopathology as a function of skin type.
 
Because this study is purely observational, there are no established quantitative endpoints.

Number of subjects	Up to 120 subjects
Inclusion Criteria	
Subjects, ages 2 – 90 years old.
 
Subject, or guardian, if applicable, must be willing to provide written informed consent prior to enrollment and agree to comply with protocol requirements. If applicable, child must be willing to provide written assent prior to enrollment and agree to comply with protocol requirements.

Study summary

Subject or guardian, if applicable, must have sufficient mental capacity to understand the Informed Consent and provide clinically relevant and reliable feedback regarding their experience with the device.

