1.4.3 Risk versus benefits

The minor risks associated with this study are outweighed by the scientific knowledge to be gained about a new imaging technology that may decrease the need to invasively biopsy patients in the future.

2 Investigator(s) and other study personnel

Whenever the term 'Investigator' is noted in the protocol text, it may refer to either the Principal Investigator at the site, or an appropriately qualified, trained, and delegated individual of the investigational site.

The study sponsor, termed 'Sponsor', is identified on the title page of this protocol, and also serves as the Sponsor-Investigator. The Sponsor will select qualified Investigators from within the organization, obtain signed study agreements, and provide the Investigators with the information necessary to conduct the study. Training on the *VioTM* procedure will occur.

The Principal Investigator must sign the protocol signature sheet before subject recruitment may start at the respective center. Likewise, all protocol amendments/integrated protocols must be signed and dated by the Principal Investigator before coming into effect at the respective center.

A complete list of all participating centers and their Investigators, as well as all required signature documents, will be maintained in the Sponsor-Investigator study file.

All other study personnel not included in this section are identified in a separate personnel list (not part of this clinical study protocol) as appropriate. This list will be updated as needed.

3 Study objectives

The overall objective of this study is to investigate the potential for the *VioTM* to display microscopic skin structure in people of different age, sex, race, and skin health.

3.1.1 Aim 1

Quantify imaging performance in various types of skin, which may include estimated in vivo resolution and imaging depth. Various types of skin includes skin of different people, skin in different locations on the body, and skin with skin disease, including basal cell carcinoma.

3.1.2 Aim 2

Qualitatively evaluate image quality and interpretability by physicians trained in dermatopathology as a function of skin type.

A large rectangular area of the page has been completely blacked out with a solid black redaction mark, obscuring several paragraphs of text.

The safety of device usage will also be evaluated by monitoring adverse events as described in Section 9.

4 Study design

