8.2 Statistical methods

The primary analysis involves the quantification of imaging performance of the *VioTM* as a function of skin type, location (e.g., forearm, ear, nose), and health of skin. Because group sizes are small, statistical comparisons are unlikely to be significant. Still, data from this study will be important for planning statistically robust future studies. As a secondary aim, image performance will also be qualitatively evaluated by physicians trained in dermatopathology interpretation. Interim analyses are not planned.

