8.3 Subject population(s) for analysis

All eligible subjects that are imaged will be included in the primary analysis according to the Aims outlined in Section 3. Non-primary analyses such as subject response to the procedure, occurrence of image artifacts, or typical reasons for screen failures may be reported for all subjects who consented to the study, or any defined subset of consented subjects.

9 Safety and adverse events

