9.2.2 Assessments and documentation of adverse events

The Sponsor-Investigator must collect all AEs for each subject from the time of the start of device procedure preparation up to 1 week following the end of subject study participation, whether or

not deemed related to the investigational device or procedure. All AE data will be recorded on the CRF.

All AEs will be followed until the event has subsided or, in case of permanent impairment, until the event stabilizes, and the overall clinical outcome has been ascertained.

The Sponsor-Investigator must document all device failures, malfunctions, and use errors, including the assessment whether the event is considered a near incident (ADE) using the CRF.

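### After the visit, AE collection for the required week rests on passive self-report, so 'no AE' cannot be told apart from 'no reply'

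*Combined protocol and SAP*

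**What the plan says.** Section 9.2.2 sets the duty, which falls on the sponsor acting as investigator. That party "must collect all AEs for each subject from the time of the start of device procedure preparation up to 1 week following the end". The end meant there is when participation finishes, and events count whether or not they are thought to be related.

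Section 4.1 gives the means. On site, "Subjects will be monitored for AEs during and immediately following the procedure". After that, "Subjects will be requested to self-report any AEs for up to seven days following the procedure". The visible text describes no scheduled call, message, visit, diary or day-7 status entry.

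On records, Section 10.2 makes the CRF the source document and has AE information entered when the need arises. Section 7.3 documents completion when participation ends, which is before the follow-up week has run. The outcome code for unknown in Section 9.2.1 describes an AE already recorded; it does not cover a subject whose 7-day status is missing.

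On use, Section 3 states: "The safety of device usage will also be evaluated by monitoring adverse events as described in Section 9". The Study summary adds: "Because this study is purely observational, there are no established quantitative endpoints". Section 8.2 makes imaging performance the primary analysis. Section 8.3 says that non-primary results "may be reported for all subjects who consented to the study, or any defined subset of consented subjects", without a rule for subjects who lack follow-up information.

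**The concern.** The duty covers all AEs in each subject, but the method for the follow-up week depends on the subject choosing to make contact. Nothing prompts a reply, and nothing records that the week was covered. A quiet week and a lost contact look the same on the CRF.

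Section 1.4.2 names contact dermatitis, infection and contusion among the possible harms. It does not say when they would appear, but some could become apparent after the subject has left. The safety review in Section 9.4 can be triggered by an increased frequency of events, and the medical monitor in Section 9.5 works from AE reports; both need the reports to arrive. Subjects may be as young as 2 years, yet the request in Section 4.1 is addressed to subjects and does not mention guardians. If the study later states that few or no AEs occurred within a week, a reader could not tell how many subjects that statement covers.

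**Working it through.** **The plan's own figure.** The only computed figure is the sample size in Section 8.1: 2 × 2 × 5 × 5 = 100 cells plus overhead = 120. This reproduces if the overhead, which is not quantified, is taken as 20. The plan states no AE rate, safety precision or power, so there is no safety figure to reproduce.

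**The two sections side by side.**
- Who: each subject (9.2.2); each subject is asked (4.1).
- What: all AEs must be collected (9.2.2); AEs are reported if the subject chooses to (4.1).
- Until when: one week after the end of participation (9.2.2); seven days after the procedure (4.1). These differ for a subject with several visits, which Section 7.3 and the Study summary allow although Section 4.1 describes a single session.
- Proof of completeness: none visible in either.

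**Illustration of size.** Inputs:
- n = 120, the maximum in Section 4.1.
- p, the true proportion of subjects with an AE (assumed).
- f, the share of AEs seen on site (assumed).
- s, the share of later AEs that are self-reported (assumed).

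The overall share captured is c = f + (1 − f) × s, and the proportion observed is p × c if silent subjects are counted as event-free. With zero events observed, the one-sided 95% upper bound on p is (1 − 0.05^(1/n)) / c. At n = 120 and c = 1 this is 1 − 0.05^(1/120) = 2.47%.

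| Late reporting s | f = 0: c, bound | f = 0.5: c, bound | f = 0.8: c, bound |
|---|---|---|---|
| 1 | 100%, 2.5% | 100%, 2.5% | 100%, 2.5% |
| 0.8 | 80%, 3.1% | 90%, 2.7% | 96%, 2.6% |
| 0.5 | 50%, 4.9% | 75%, 3.3% | 90%, 2.7% |
| 0.3 | 30%, 8.2% | 65%, 3.8% | 86%, 2.9% |

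Example: s = 0.5 and f = 0.5 give c = 0.5 + 0.5 × 0.5 = 0.75, and 2.47% / 0.75 = 3.3%.

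The chance of seeing nothing also rises. With p = 2% and full capture, the probability of zero observed events is 0.98^120 = 8.9%. With f = 0 and s = 0.5 it is 0.99^120 = 29.9%.

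**The case against.** The strongest reply is that the sections do not contradict each other. Self-report is a legitimate means of collection, the request goes to every subject, and Section 5.1 requires agreement to comply and the capacity to give reliable feedback on the device. This stands as far as it goes: the defect is that completeness is not verified, not that collection is impossible.

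A reader might infer that silence is counted as 'no event' and that the study's AE rate is therefore biased downward. The documents do not support that. No section says how a silent subject is recorded or counted, and the plan defines no AE rate, denominator or bound. AEs feed individual assessment, reporting to the IRB and authorities, medical monitoring and ad hoc review. The downward direction follows only if someone later forms a proportion with silent subjects kept in the denominator as event-free.

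On-site monitoring also limits the loss. The f = 0 column is close to a worst case; with half or more of AEs seen on site the effect is clearly smaller. Section 1.4.2 describes the risk as no more than minimal and gives a mitigation for each named harm.

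Finally, part of the text cannot be seen. Several paragraphs are blacked out just before the safety sentence in Section 3, further text is redacted in Section 6, Figure 3 is not shown, and the visible numbering goes from 7.4 to 7.6. A follow-up contact could be described there, so its absence can be stated only for the visible text.

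**Conclusion.** The gap holds for the visible text. Section 9.2.2 asks for complete collection to one week, and after the visit the plan relies on a passive method with no record that separates no AE from no reply. Followed exactly, that method risks under-ascertainment in the 7-day window.

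The size cannot be determined from the documents. Over the assumed ranges above, the zero-event upper bound at n = 120 runs from 2.5% to 8.2%. The central illustrations, at 50% late reporting, are 4.9% with no AEs seen on site and 3.3% with half seen. Fewer than 120 subjects would raise all of these.

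The point does not touch the primary analysis of imaging performance. It is worth acting on because safety is a stated evaluation, the change is cheap, and missing day-7 status is hard to recover later.

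**What to change.** In Section 4.1, replace the self-report sentence with one scheduled contact about 7 days after each session, by email, text or call, made to the guardian for children, with a yes/no AE question. Keep self-report open in between. Record AE, no AE or not reached on the CRF.

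Report in-session AEs over all imaged subjects. For the 7-day window, report the AEs together with the number of subjects whose status was ascertained and the number not reached. Count any AE reported earlier even if the day-7 contact is missed. Align the windows in Sections 4.1 and 9.2.2 for subjects with several visits.

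Declaring a denominator of confirmed responders without adding a contact would not work: only subjects with events would be confirmed, so the proportion would be 100%, or undefined with zero events.

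If redacted text or Figure 3 already describes a contact, Section 4.1 need only cite it, provided the three-way status is recorded.

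The cost is a little time from existing staff per session, routed through the designated custodian because Section 10.1 restricts access to names, and possibly a less favourable AE statement. No visit or imaging procedure is added.

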4.2 Justification for clinical study design

Initial human testing (described in Section 1.3) demonstrates decades of scientific research confirming successful nonlinear imaging of skin *in vivo*. The study described herein will provide observational evidence for the effectiveness of the *VioTM*, a miniaturized nonlinear microscope, to display features of skin structure as well.

In this study, we plan to gather feasibility data for future studies. This feasibility data will likely inform future clinical investigations of skin disease diagnosis and may assist with sample size calculations.

5 Subject selection and withdrawal

The target patient population is composed of male and female adults and children that meet eligibility criteria described in Sections 5.1.1 through 5.1.5.

5.1 Inclusion criteria

- Subjects, ages 2 – 90 years old.
- Subject or guardian, if applicable, must be willing to provide written informed consent prior to enrollment and agree to comply with protocol requirements. If applicable, child must be willing to provide written assent prior to enrollment and agree to comply with protocol requirements.
- Subject or guardian, if applicable, must have sufficient mental capacity to understand the Informed Consent and provide clinically relevant and reliable feedback regarding their experience with the device.
- Subject and guardian, if applicable, must comply with the protocol requirements.
- Subject or guardian, if applicable, must agree that anonymized personal data will be made available to Study Sponsor and requisite regional and international regulatory bodies.

5.2 Exclusion criteria

- Subjects that meet any of the following exclusion criteria will not participate in the study.
- Any general health condition or systemic disease that may represent, in the opinion of the Principal Investigator, a potential increased risk associated with device use.
- Currently infected with a communicable skin infection that may represent, in the opinion of the Investigator, a potential increased risk to other subjects or users of the device (e.g., shingles or methicillin-resistant *S. aureus*), which does not likely include local and non-pathogenic or minimally pathogenic infections distant from the imaging location(s) (e.g., warts, acne)
- Any known allergies to any materials used in the preparation of skin and/or device use.
- Has a temporary or permanent electrical implanted medical device

5.3 Subject recruitment and screening

Subjects will be recruited for the study using advertisements communicated with flyers, pamphlets, classified ads in local newspapers, electronic posts to sites such as Craigslist.com or SUPost.com, emails to listservs, word-of-mouth, and/or physician referral/recruitment. If a subject is recruited by physician, with permission of the possible subject, the physician may optionally mark a region of interest of skin to be investigated to assist the other study staff (e.g., with a small bandage or a small mark with skin marker). This marking process will likely occur before informed consent for the study has been received because the full explanation of the study will be presented in a separate space without the referring physician present. The marking is temporary; informed consent for the study will be conducted within an hour of marking placement.

After the subject provides written informed consent, the subject will be screened by the Investigator or designee using the protocol defined inclusion and exclusion criteria to determine study eligibility.

5.4 Early withdrawal of subjects

Subjects may be withdrawn from the study prior to the expected completion of that subject for the following reasons:

- Any reason that, in the opinion of the Investigator, poses a safety hazard to the subject
- Failure of subject to adhere to protocol requirements, including but not limited to
 - Inability to stay awake in order to follow instructions
 - Inability to stay still for high quality images
 - Not following Investigator's or designee's instructions
- Subject consent withdrawal

If imaging has already begun when the subject is withdrawn, the laser will be shuttered or turned off and imaging will cease. Abrupt termination of the study will not affect subject safety. Any data collected until withdrawal may still be included in study results.

6 Inclusion of vulnerable populations

6.1 Children

6.1.1 Reason(s) for choosing this subject population

Children have been selected as a vulnerable population that may be included in this study because children as a group may particularly benefit from the results of the study, although individual child subjects will not benefit.

The noninvasive technology presented in this protocol may one day reduce the need for invasive skin biopsies. While a biopsy of the skin with local anesthetic is typically considered a minor surgical procedure for adults, for non-assenting or frightened children, skin biopsies may require the use of general anesthesia, sedation²⁰, or even physical restraint. Participation of children in early feasibility studies such as the one detailed in this protocol will better ensure that noninvasive imaging technology is applicable to this important population.

Although children will be invited to participate, there are no required enrollment targets for children, and the study may be successfully completed without the participation of children.

6.1.2 Level of risk

The risk of this protocol is no more than minimal and is the same for the population of children as for the larger eligible population.

[figure not shown]
6.1.3 Consent, assent, and coercion

Children may not have the cognitive ability to fully understand the study, risks of the study, and that participation is voluntary, which is why they are considered to be a vulnerable population.

6.1.4 Consenting plan and special protections

Children shall be eligible for this protocol. The group benefits to children of this human research, with special protections, outweigh children's diminished consenting capacity, especially since the risks of the study are no more than minimal.

In order for a child to participate, a parent or legal guardian must provide permission and the child must assent. The full study will be described to the parent or guardian using the consent form. Assent shall be appropriate for the child's age: (1) children under age 7 will be asked to verbally assent, if possible and (2) children aged 7-17 will read (or be read) the child's assent form, and will sign the assent form. Every child will have the option to read the entire consent form if he or she wishes and is able. All children will have the study explained to them at their understanding level by the Investigator.

1. **What is the primary purpose of the proposed legislation?**

1. **What is the primary purpose of the proposed legislation?**

For more information, visit www.ams.org.

1. **What is the primary purpose of the study?** (Please check one box)

■ [REDACTED]

11. **What is the primary purpose of the *Journal of Clinical Endocrinology and Metabolism*?**

10. **What is the primary purpose of the *Journal of Clinical Endocrinology and Metabolism*?**

■ XXXXXXXXXX

1. **What is the primary purpose of the proposed legislation?**

1 | Page

7 Study procedures

Study procedures described below are also shown in schematic form in Figure 3.

7.1 *Informed consent, screening, & baseline*

7.1.1 **Consent**

The subject will come to the investigation space where the *VioTM* is set up and may be escorted by study staff between referring physician and the research space, which may be in the same building. The Investigator(s) will fully explain the nature and purpose of the research and procedures, answer questions from the subject, and will obtain the proper signatures of subject and/or guardian on the informed consent form. If, in the Investigator's judgment, the subject or guardian cannot fully understand the procedure or communicate understanding, consent or permission, if applicable, will not be obtained and the subject will not be eligible for the study.

All relevant information on the study will be summarized in an integrated subject information sheet and informed consent form (ICF). Based on this subject information sheet, the Investigator or designee will explain all relevant aspects of the study to each subject and guardian, if applicable, prior to entry into the study (i.e., any study-specific data is recorded on study-specific forms).

Each subject and guardian, if applicable, will have ample time and opportunity to ask questions and will be informed about the right to withdraw from the study at any time without any disadvantage and without having to provide reasons for this decision. Only if the subject and/or guardian agrees to sign the ICF and has done so, may the subject enter the study. Additionally, the Investigator will personally sign and date the form. The subject or guardian, if applicable, will receive a copy of the signed and dated ICF. An assent section will be included as part of the ICF for obtaining assent from children age 7-17.

The ICF and any other written information provided to subjects and guardians will be revised whenever important new information becomes available that may be relevant to the subject's consent, or there is an amendment to the protocol that necessitates a change to the content of the subject information and/or the written ICF.

